An Open-label Dose Escalation Study of an Adeno-associated Virus Vector (scAAV2-P1ND4v2) for Gene Therapy of Leber's Hereditary Optic Neuropathy (LHON) caused by the G11778 mutation in mitochondrial DNA.

NCT02161380

Date: February 9, 2019. IRB 20140248.

1) **Protocol Title**

An Open-label Dose Escalation Study of an Adeno-associated Virus Vector (scAAV2-P1ND4v2) for Gene Therapy of Leber's Hereditary Optic Neuropathy (LHON) caused by the G11778 mutation in mitochondrial DNA

SHORT TITLE: Leber's hereditary optic neuropathy (LHON): Gene Therapy Clinical Trial

IND NO.: 15941

IND SPONSOR: [REDACTED]

- LHON: Gene Therapy Clinical Trial is registered on the Clinical Trials.gov website (<http://clinicaltrials.gov>). Clinicaltrials.gov number: NCT02161380

2) **IRB Review History***

N/A

3) **Objectives***

Our goal is to test safety.

The **purpose** of this dose-escalation study is to assess the safety and tolerability of scAAV2-P1ND4v2 (abbreviated as AAV-ND4) gene replacement therapy in subjects confirmed with the G11778A mutation in mtDNA responsible for Leber's Hereditary Optic Neuropathy. Ocular and systemic toxicity will be assessed following vector administration to determine if there are adverse changes that may be associated with vector administration.

This first-in-man (FIM) clinical trial will assess safety, tolerability, and potentially efficacy of a single intravitreal injection in patient groups reflecting the acute, presymptomatic and chronic stages and manifestation of the LHON disease.

Aim 1. To Evaluate the Safety of AAV-ND4 in subjects with long-standing bilateral acuity loss (Group 1). Phase I will consist of an open-label, unilateral single-dose, intravitreal injection of AAV-ND4 per subject in a dose-escalation study investigating the safety of four vector doses (Low: 1.18×10^9 vg*, Medium: 5.81×10^9 vg*(*based on CHOP titers as recommended by FDA), High: 2.40×10^{10} vg and Higher: 1×10^{11} vg) in subjects with molecularly confirmed G11778A-mutated mitochondrial DNA. The bilateral chronic group will include patients with ≥ 12 months since onset in one eye and at least 6 months onset in the more recently affected eye. Both eyes must have acuity reduced to ≤ 35 letters. If both eyes have ≥ 12 months since onset, the eye with worse visual acuity will be

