injected. If both eyes have the same acuity the eye with longest onset will be injected. If one eye has <12 months and >6month since onset and the difference in acuity between the eyes is ≤ 10 letters, the eye with ≥ 12 months will be injected. If eyes have an acuity difference >10 letters, the eye with worse acuity will be injected.

Aim 2. To Evaluate the Safety of AAV-ND4 in subjects with acute (<12 months) bilateral loss of visual acuity to ≤ 35 ETDRS letters (Snellen = 20/200) (Group 2). The eye with worse acuity will be injected.

Aim 3. To Evaluate the Safety of AAV-ND4 in subjects with unilateral loss of acuity to ≤ 35 ETDRS letters, but who have “good acuity” ≥ 70 letters (20/40 Snellen) in the contralateral eye (Group 3). The eye with better acuity will be selected for injection.

For each group, administration of study drug will follow an adaptive plan to identify the maximum tolerated dose. If none of the three subjects at a given dose level develops a major toxicity, the next cohort will receive the next higher dose. We will wait a minimum of 6 weeks between injections of the same dose in successive subjects, and will wait until 3 months after the last subject is injected with this dose before moving to the cohort receiving the next higher dose. We will test the lowest dose first in 3 subjects of Aim 1, before moving on to testing this low dose in Aim 2, then lastly in Aim 3. Safety will be monitored for loss of 15 letters in Aims 1 and 2, but a difference of 15 letters worse in the treated eyes relative to untreated eyes for Aim 3. If acuity, and visual field testing demonstrate no toxicity in Aims 1 and 2, we will proceed with Aim 3.

The **objective** of this proposed clinical trial is to evaluate the safety of mitochondrially targeted ND4 gene therapy with the adenoassociated viral vector in appropriate LHON patients in a Phase I clinical trial. If warranted by the results of the Phase I trial, another aim will be to obtain a preliminary estimate of the therapy’s efficacy. We provide a summary of the extensive preclinical testing in relevant rodent animal models to support the efficacy of the approach proposed in this clinical trial.

The **primary hypothesis** being tested is there will be no systemic toxicity or loss of vision to No Light Perception in the injected eye.

4) **Background***

Background and Significance

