9. History of neurodegenerative conditions (e.g. multiple sclerosis, neuromyelitis optica, Parkinson disease)
10. History of autoimmune conditions (e.g. systemic lupus erythematosus)
11. Systemic diseases having ocular manifestations likely to confound assessment of study resultsHistory of cancer within five years other than localized basal or squamous cell carcinoma not near the orbital area. Patients with a prior history of cancer will need documentation from their cancer specialist that the cancer was cured at least 5 years before study entry.
12. Allergy to pupil dilating drops or narrow angles precluding safe dilation.
13. No Light Perception (NLP) vision in either eye.

, “No special populations are to be included in this research, such as children 14 years old or younger, prisoners, or pregnant women.

- **Exclude:** All subjects who are unable to consent
- **Exclude:** Children 14 years old or younger
- **Exclude:** Pregnant women

- **Exclude:** Prisoners

6) **Number of Subjects***

Number of Study Centers: One (1), Bascom Palmer Eye Institute, University of Miami, Miami, FL.

For each group patient recruitment will consist of 3 cohorts, until the last cohort which will consist of both Group I and III individuals.

Table 1 Proposed Sample Size

	Low-dose (1.18×10^9 vg)*	Medium dose (5.81×10^9 vg)*	High dose (2.40×10^{10} vg)	Higher dose (1×10^{11} vg)
Group I	3	3	3	
Group II	3	3		3
Group III	3	3		
Group I And** Group III				3 3

*=based on CHOP titers as recommended by FDA

As summarized above, dose escalation will follow the adaptive Phase 1 plan of Rubinstein and Simon (<http://linus.nci.nih.gov/techreport/phaselctd.pdf>). At each dose, escalation will occur until 2 of 3 (or 6) injected eyes manifest the safety endpoint. (See reference for detailed description of dose escalation strategy) Table 2 of the reference contains operating characteristics of this approach. Following the algorithm of Rubinstein and Simon with three doses, the sample size could range between 3 and 18 for each group. As an example, if the true probabilities of noteworthy safety events in the proposed three doses were 0.05, 0.25, 0.5, respectively, the most likely sample sizes for each group would range between N=9 with probability 20%, N=12 with probability 54%, or N=15, with probability 22%. These sample sizes could potentially be sufficient to observe a treatment effect when compared in a matched fashion to the uninjected eyes in groups 1 and 3.

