Ancillary data analysis will include assessments of the changes in acuity, visual fields, and OCT RNFL thickness as well as correlations between these measurements to the limited extent that this can be studied with such a small sample size. Assuming that the earlier the stage, the more likely the benefit of treatment, we will examine and develop outcomes that can be used in later phases and other trials that could include a wide range of these patients before the onset of permanent visual deficits.

Evaluations of Efficacy in a phase I trial.

Patients with molecularly confirmed G11778A mitochondrial DNA will be recruited into one of 3 groups.

	Low-dose (1.18×10^9 vg)	Medium dose (5.81×10^9 vg)	High dose (2.40×10^{10} vg)	Higher dose (1×10^{11} vg)
Group I	3	3	3	
Group II	3	3		3
Group III	3	3		3

The certified technician performing the visual acuity assessments will be masked to treatment. The elimination of improvement to ≥ 70 letters from the efficacy endpoint increases the likelihood of a success by natural history and correspondingly decreases power. To obtain the requisite patient numbers needed to complete the efficacy

assessments, we will submit for another U10 for phase II, if phase I safety assessment supports further investigation. Our previous power estimates were based on improvement by 15 letters and acuity of 20/40 and included both best and worst eyes of patients (Aim 1 and 2). The new endpoint, which drops the latter requirement, is more common in natural history but is assessed only on the 31 worst eyes eligible for Aim 1 and Aim 2. We include the upper 95% confidence intervals along with the point estimates as recommended.

Power for detecting 15 letter improvement with N=9 in group I

		Treatment Efficacy		
Natural History Estimate		50%	75%	95%
Point:	9%	Power 35%	83%	>95%
Upper 95% CI:	28%	Power 13%	41%	92%

Power for detecting 15 letter improvement with N=9 in group 3

		Treatment Efficacy		
Natural History Estimate		50%	75%	95%
Point:	33%	Power 9%	30%	88%
Upper 95% CI:	70%	Power NA	NA	17%

Sample size for 80% (90%) power to detect a 15 letter improvement in group I

		Treatment Efficacy		
Natural History Estimate		50%	75%	95%
Point:	9%	N 18 (22)	9 (10)	6 (6)
Upper 95% CI:	28%	N 76 (100)	18 (21)	9 (9)

Sample size for 80% (90%) power to detect a 15 letter improvement in group 3

		Treatment Efficacy		
Natural History Estimate		50%	75%	95%
Point:	33%	N 130 (175)	22 (27)	9 (11)
Upper 95% CI:	70%	N NA	NA	34 (41)

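### Group I's two efficacy yardsticks, the worst-eye natural-history rate and the uninjected fellow eye, do not follow the trial's own rule for choosing the injected eye

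*Combined protocol and SAP*

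**What the plan says.** **Eye selection (Section 3, Objectives, Aim 1).** Group I takes patients with "≥ 12 months since onset in one eye and at least 6 months onset in the more recently affected eye", both eyes at 35 letters or fewer. The choice of eye then has three branches.

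- Both eyes at 12 months or more: "If both eyes have ≥ 12 months since onset, the eye with worse visual acuity will be" injected. If acuity is equal, the eye with the longer history is injected.
- One eye between 6 and 12 months, acuity close: if "the difference in acuity between the eyes is ≤ 10 letters, the eye with ≥ 12 months will be injected".
- Acuity further apart: "If eyes have an acuity difference >10 letters, the eye with worse acuity will be injected".

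**Natural-history yardstick (Section 12, Evaluations of Efficacy in a phase I trial).** The 15-letter improvement endpoint "is assessed only on the 31 worst eyes eligible for Aim 1 and Aim 2". The Group I tables use a rate of 9% with an upper 95% limit of 28%, for example under "Power for detecting 15 letter improvement with N=9 in group I".

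**Fellow-eye yardstick (Section 6, Number of Subjects).** The sample sizes might be enough to show a treatment effect "when compared in a matched fashion to the uninjected eyes in groups 1 and 3".

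Nothing in the document re-selects the natural-history eyes by the Aim 1 rule, and nothing adjusts the fellow-eye contrast for time since onset or baseline acuity. Measuring change from Baseline 2 (Section 12, Data Analysis) deals with regression to the mean only.

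**The concern.** A yardstick for an uncontrolled treated group should describe what the injected eyes would have done without treatment. Here the eye is chosen by one rule in the trial and by another in the natural-history series. The within-patient control is whichever eye the rule leaves over. The document itself treats stage as relevant: Section 4 says visual decline can continue for months, and Section 12 assumes that earlier-stage eyes benefit more. If eyes at 6 to 12 months behave differently from settled eyes, part of any Group I difference would come from the selection rule and not from the vector. Section 3 hopes for a preliminary efficacy estimate, and Section 12 foresees a phase II application, so the Group I figures may be carried forward.

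**Working it through.** **1. The branches side by side (Section 3, Aim 1)**

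| Group I patient | Injected eye | Fellow eye | Does a worst-eye rate describe the injected eye? | Same onset stage in the pair? |
|---|---|---|---|---|
| Both eyes ≥12 months, unequal acuity | Worse | Better, ≥12 months | Yes | Yes, but acuity differs by design |
| One eye 6–12 months, difference ≤10 letters | The ≥12-month eye | The 6–12-month eye | Only if the ≥12-month eye is not the better one | No |
| One eye 6–12 months, difference >10 letters | Worse, which may be either eye | The other | Yes | No |

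The natural-history mismatch is confined to part of the second row. The fellow-eye mismatch covers the second and third rows, with opposite orientations possible.

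**2. The plan's own figures**

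Inputs: 9% and 28% against 50%, 75% and 95% (Section 12). Alpha and the test are not stated; I assumed two-sided 5%, two equal independent groups and pooled variance:

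n = [1.960·√(2p̄(1−p̄)) + z_power·√(p₁(1−p₁)+p₂(1−p₂))]² / (p₂−p₁)²

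For 9% against 50% at 80% power: (1.960×0.645 + 0.842×0.576)² / 0.41² = 18.2, so 19; the plan prints 18.

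| Rate | Printed N, 80% (90%) | Computed |
|---|---|---|
| 9% | 18 (22), 9 (10), 6 (6) | 19 (24), 8 (10), 4 (5) |
| 28% | 76 (100), 18 (21), 9 (9) | 76 (102), 17 (22), 7 (9) |

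All 12 agree within 2. The N=9 power rows did not reproduce as a set under any one method tried; that is a separate matter and nothing here relies on them.

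The 9% cannot be a count out of 31 (2/31 = 6.5%, 3/31 = 9.7%). With exact limits, 2/23 fits: 8.7%, upper limit 28.0%. The denominator is my inference. If it is right, one eye whose outcome changes on re-selection moves the rate to 1/23 = 4.3% or 3/23 = 13.0%.

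**3. Natural-history rate under the trial's rule**

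Let s be the share of Aim 1 natural-history patients whose counted eye is a 6–12-month eye that the rule would not inject, p the improvement rate of those eyes, and r the rate in rule-selected eyes, taken as equal across patients. Then 9% = (1−s)r + s·p, so r = (9% − s·p)/(1−s). The documents give neither s nor p. For s = 10% and 20%, assumed:

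| Assumed p | r at s = 10% | r at s = 20% |
|---|---|---|
| 5% | 9.4% | 10.0% |
| 9% | 9.0% | 9.0% |
| 15% | 8.3% | 7.5% |
| 33% | 6.3% | 3.0% |

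The 33% is printed for group 3, not for 6–12-month eyes, and serves only as an outer illustration. The corrected rate can fall on either side of 9%.

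For scale, N for 80% power at 50% efficacy by the formula above is 15, 19 and 27 at no-effect rates of 5%, 9% and 15%.

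**4. Fellow-eye contrast with an inert vector**

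Let d be the improvement rate of 6–12-month eyes minus that of ≥12-month eyes, a the share of pairs with a 6–12-month fellow eye, and b the share with a 6–12-month injected eye. Ignoring acuity, the expected difference, injected minus fellow, is (b − a)·d.

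For illustration take d = 28% − 9% = 19 points (assumed; 28% is a confidence limit, not a rate for recent eyes):

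- a = 3/9, b = 0: −6.3 points
- a = b: 0
- a = 0, b = 3/9: +6.3 points

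If recent eyes do worse than settled ones, d is negative and every sign reverses.

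**The case against.** The strongest case against is that this matters little. The trial's goal is safety. Section 12 plans descriptive statistics with 95% confidence intervals, calls the acuity analysis ancillary and leaves completion of the efficacy assessment to phase II. Section 6 says only that a matched comparison might suffice. No test against either yardstick is specified, and the tables already span 9% to 28%. The natural-history mismatch needs a recent eye, acuity within 10 letters and a better settled eye, all in one patient. The entry limits (at least 6 months from onset, 35 letters or fewer in both eyes) narrow the gap between stages.

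Most of this stands and keeps the point modest. It does not remove it. The 9% to 28% span reflects sampling error in worst eyes and does not address which eye was counted. The fellow-eye mismatch reaches every patient with a 6-to-12-month eye.

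A reader might infer more: that the rule hides a true effect because recent eyes recover more often, by 24 points per affected pair (9% against 33%). The documents do not support that. In the branch above 10 letters the recent eye can be the injected one, which reverses the sign. The 33% belongs to another group. Section 4's account of continuing decline points the other way. And 9% cannot serve as the settled-eye rate in an argument that it is contaminated by recent eyes.

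**Conclusion.** The point holds as a mismatch of definitions. For some Group I patients the worst-eye rate can count an eye that the trial would not inject. For every Group I patient with a 6-to-12-month eye, the matched contrast compares eyes at different times since onset. Direction and size are not determined: they depend on the share of such patients, the orientation of their pairs and the improvement rate of 6-to-12-month eyes, none of which the documents give. The figures above are illustrations under stated assumptions. It would be too strong to conclude that the Group I sample sizes are wrong, since they reproduce within 2 from the rates the plan chose. The consequence is limited to interpreting a secondary, descriptive efficacy signal, but the correction is cheap and worth making.

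**What to change.** In Section 12, re-tabulate the natural-history rate and its upper 95% limit on the eye that the Aim 1 rule would have selected in each Aim 1-eligible natural-history patient. State the numerator and denominator. Use that rate in the Group I power and sample-size tables and in any comparison with Group I.

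For the fellow-eye contrast, keep all pairs. Report separately the pairs with both eyes at 12 months or more and the pairs with one eye at 6 to 12 months, the latter split by which eye was injected. Give baseline acuity of both eyes throughout. Restricting the contrast to pairs with both eyes at 12 months or more is not recommended: it takes pairs from a group planned at nine in Section 12, and with unequal acuity the injected eye is still the worse one.

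Cost: a small re-analysis and a few sentences in Section 12. This assumes that the 31 eyes come from the completed natural-history study described in Section 24, so that the data are in hand. The strata will be very small, and the re-tabulated rate may be less favourable than 9%. No change to dosing, eligibility, eye selection or visits is involved.
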